9.7.5.3 Neurological Examination

A complete neurological examination will include level of consciousness, speech, language, cranial nerves, motor strength, motor tone, abnormal movements, reflexes, upper extremity sensation, lower extremity sensations, gait, Romberg, nystagmus, and coordination.

9.7.5.4 Electrocardiogram

For the first infusion of BMN 190, continuous ECG monitoring (3- or 5-lead) will be performed for all subjects. The ECG should begin 15 (\pm 5 minutes) prior to infusion start, continue through infusion of BMN 190, and end after infusion of flushing solution. In the event that the subject has already received the first infusion of BMN 190, the next infusion will be monitored as above. If a 12-lead ECG is required during this time, continuous monitoring should be interrupted in order to obtain the 12-lead ECG.

A standard ECG (12-lead), including heart rate, rhythm, intervals, axis, conduction defects, and anatomic abnormalities. ECG will be performed 30 (\pm 5) minutes after infusion end at the first infusion and every 24 weeks thereafter. In patients with present or past bradycardia, conduction disorders, or with structural heart disease, an ECG will be performed within 30 minutes before the start of infusion (\pm 5 minutes), at 2 hours (\pm 15 minutes) during infusion, within 30 (\pm 5) minutes after infusion end, and 12 hours (\pm 3 hours) after infusion end for each study drug infusion.

If a clinically significant abnormality is noted, the investigator or designee will evaluate whether study enrollment or continuation is appropriate; a clinically significant abnormality will be recorded under Medical History during Screening and as an AE thereafter.

9.7.5.5 Pregnancy Testing

At Screening and at any time during the study, a female subject judged by the investigator to be of childbearing potential (as defined by onset of menses) will be tested for pregnancy with a urine pregnancy test; additional urine tests will be performed whenever pregnancy is in question. A serum pregnancy test will be performed if a urine test result is positive or equivocal.

10 REPORTING ADVERSE EVENTS

10.1 Safety Parameters and Definitions

Safety assessments will consist of monitoring and recording protocol-defined AEs and SAEs; measurement of protocol-specified hematology, clinical chemistry, and urinalysis variables; measurement of protocol-specified vital signs; and other protocol-defined events of special interest that are deemed critical to the safety evaluation of the study drug.

10.1.1 Adverse Events

For this protocol, a reportable adverse event (AE) is any untoward medical occurrence (e.g., sign, symptom, illness, disease or injury) in a patient administered the study-drug or other protocol-imposed intervention, regardless of attribution. This includes the following:

- AEs not previously observed in the subject that emerge during the course of the study.
- Pre-existing medical conditions judged by the Investigator to have worsened in severity or frequency or changed in character during the study.
- Complications that occur as a result of non-drug protocol-imposed interventions (e.g., AEs related to screening procedures, medication washout, or no-treatment run-in).

An adverse drug reaction is any AE for which there is a reasonable possibility that the study-drug caused the AE. "Reasonable possibility" means there is evidence to suggest a causal relationship between the study-drug and the AE.

Whenever possible, it is preferable to record a diagnosis as the AE term rather than a series of terms relating to a diagnosis.

10.1.2 Serious Adverse Events

A serious adverse event (SAE) is any untoward medical occurrence that at any dose meets 1 or more of the following criteria:

- Is fatal
- Is life threatening

Note: Life-threatening refers to an event that places the patient at immediate risk of death. This definition does not include a reaction that, had it occurred in a more severe form, might have caused death.

- Requires or prolongs inpatient hospitalization.
- Results in persistent or significant disability or incapacity

BOMARIN 190-203 Amendment 6

- Is a congenital anomaly or birth defect in the child or fetus of a patient exposed to IP prior to conception or during pregnancy
- Is an important medical event or reaction that, based on medical judgment, may jeopardize the patient or require intervention to prevent one of the above consequences (e.g. anaphylaxis)

All adverse events that do not meet any of the criteria for SAEs should be regarded as non-serious AEs

10.1.3 Adverse Events of Special Interest (AEoSI)

The following AEoSI need to be reported to the Sponsor within 24 hours of site awareness, irrespective of seriousness, severity or causality, to facilitate real-time monitoring and assessment:

- Status epilepticus
- Hydrocephalus (communicating and non-communicating)
- Meningitis
- Unexpected rapid decline on CLN2 scale not attributable to other causes
- Hypersensitivity
- Temporally-related events
- Device-related events (e.g., infection, prophylactic ICV replacement, malfunction with an associated AE such as leaking reservoir or a problem that ends the administration of study drug for that visit, etc).
 - All removed or replaced implantable ICV devices must be returned to BioMarin in order to evaluate the material integrity of the reservoir, and all other devices (as described in the protocol Pharmacy Manual) except for infusion pumps, should also be returned.
- Cardiovascular events
- ECG adverse events

10.2 Methods and Timing for Capturing and Assessing Safety Parameters

10.2.1 Adverse Event Reporting Period

The study AE/SAE/AEoSI/pregnancy reporting period is as follows:

• After informed consent and prior to ICV access device implantation: all SAEs related to study-mandated procedures

Page 71

BIOMARIN 190-203 Amendment 6

- After ICV access device implantation but before first dose: all SAEs related to study-mandated procedures and all device-related AEs, except as defined in SAE Exclusion section.
- After first dose: all AEs, SAEs, AEoSI, and pregnancies.

AE/SAE/pregnancy reporting should continue as detailed above until the safety follow-up visit occurs 6 months after the last administration of study drug. The Safety Follow-up visit is not required if a subject enrolls in an extension study or registry or otherwise continues to have access to BMN 190 within 6 months of the final infusion. For subjects who enroll into another BioMarin-sponsored study or registry, AE/SAE reporting is as follows:

- The 190-203 reporting period for new onset AEs/SAEs, pregnancies, and device related events ends when the subject receives the first dose of study drug under the new study or registry.
- Ongoing AEs related to study drug will be followed until resolution under this study.
- All ongoing SAEs, pregnancies, and device-related events will be followed until resolution under this study.

Events that started in this study and worsen after first the dose of study drug in the new study or registry will be captured as a new event under the new study. For subjects who do not participate in an extension study or registry after the last dose of study drug, the 4-week Device Safety and 6-month Safety follow-up visit will capture information regarding ongoing events at the time of the last dose or new events related to study drug.

For this study, a medical device is defined as the infusion pump and all contact parts (reservoir and catheter, needles, infusion line with filter, extension sets, and syringes) intended to be used for administration of BMN 190. Adverse events assessed by the investigator as related to the device, including malfunction, injury, or medication error, will be entered into the EDC (electronic data capture). Prophylactic replacement of the ICV must be reported as a device related event. All AEs related to the device will be reported to BPV within 24 hours using the EDC and study specific case report form(s). The reporting period for device-related events begins with reservoir implantation and ends 4 weeks following the final removal of the implanted reservoir and catheter.

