- ^w From signed ICF to first dose of study drug only SAEs related to study mandated procedures are reported. From implantation of ICV device all devices related events are reported. All AEs and SAEs will be recorded starting with the first dose of study drug in Study 190-203 until 6 months after either the last administration of study drug or the Early Termination visit. A Safety Follow-Up visit will also be performed within 6 months after the last administration of study drug or Early Termination. The 6-month Safety Follow-Up Visit will be waived for subjects who begin receiving study drug in another BioMarin-sponsored study or registry within this 6-month period. For subjects who do not participate in an extension study or registry after the last dose of study drug, the 4-week Device Safety and 6-month Safety follow-up visit will capture information regarding ongoing events at the time of the last dose or new events related to study drug.
- * Medications (prescription, over-the-counter, and herbal) and nutritional supplements taken during the 30 days before informed consent will be recorded in the eCRF at Screening. At each subsequent visit (or within 1 week of the Early Termination visit), change in any medication (dosage, frequency, new medication, or cessation) since the previous visit will be recorded in the eCRF. Any concomitant medication added or discontinued during the study should be recorded in the eCRF (or within 1 week of the Early Termination visit). Subjects may be taking anticonvulsants and medications for myoclonus, tremor, agitation, and pain. Investigators will be asked to keep these regimens constant throughout the study, unless changes are required due to lack of efficacy or toxicity. Use of non-drug therapies such as physical and occupational therapy should also be noted in the eCRF.
- ^y In the event of a suspected anaphylactic reaction, serious hypersensitivity event, or severe hypersensitivity (defined as a hypersensitivity event of Grade 3 or higher), blood samples to assess C4, serum tryptase, and total IgE will be collected within 1 hour of the event and tested; a blood sample to assess drug-specific IgE will be collected no sooner than 8 hours after the event (or before the next infusion).

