9.3.3 Removal of Subjects from Treatment or Assessment

Subjects (or their legally authorized representatives) may withdraw consent for study participation any time without prejudice; investigators must withdraw from the study any such subject. At the discretion of investigator clinical judgment, a subject may be withdrawn from the study any time. When possible, an Early Termination visit should be scheduled (Section 12.10).

It is a priority of the study to maximize study subject retention and adherence to study-specific procedures. Since study data completeness may affect integrity and accuracy of study results, any subject who suspends or discontinues study treatment should be encouraged to continue study-specific procedures for the remainder of the study. Subjects may suspend or discontinue study medication but should be encouraged to be evaluated per study-specific visit schedule and to undergo all required study procedures and assessments.

The investigator (or designee) must contact the BioMarin medical monitor when a subject discontinues from the study. BioMarin reserves the right to discontinue the study at any time for either clinical or administrative reasons and to discontinue participation of an individual investigator or study site for poor enrollment or noncompliance with the protocol or regulatory requirements.

Reasons for which the investigator or BioMarin may withdraw a subject from the study include, but are not limited to, the following:

- Subject experiences a serious or intolerable AE
- Subject develops a clinically significant laboratory abnormality
- Subject requires medication or medical procedure prohibited by the protocol
- Subject does not adhere to study requirements specified in the protocol
- Subject was erroneously admitted into the study or does not meet entry criteria

• Subject is lost to follow-up

If a subject fails to return for a scheduled visit, a documented effort must be made to determine the reason. If the subject cannot be reached by telephone, a certified letter should be sent to the subject (or the subject's legally authorized representative, if appropriate) requesting that s/he contact the investigator. A copy of this letter and any response should be kept in the study records. If the subject cannot be contacted or fails to respond, the subject will be considered lost to follow-up.

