- If two subjects experience the same NCI CTCAE v. 4.0 Grade 3 AE, or if one subject has a Grade 4 AE that, in the investigator's opinion, is not related to the underlying disease, the BioMarin medical monitor will consult the DRB to evaluate the risk/benefit of continuing the study.

Another possible AE is infection from or failure of the indwelling ICV catheter. If an infection is suspected, blood and CSF samples will be drawn for assessment. The subsequent course of therapy, which is guided by site neurosurgical standards of care, may include antibiotic therapy, catheter reposition, or catheter withdrawal. If BMN 190 treatment is suspended, BMN 190 may resume if no more than 4 consecutive missed doses elapse after the last given dose.

If BMN 190 treatment is suspended for any reason, study participation may resume if no more than 4 consecutive doses were missed from the prior given dose.

If two or more subjects experience unacceptable drug-related toxicity, BioMarin may suspend further enrollment in the study pending a review of the data and upon consultation with the DRB. Depending on the nature and severity of the unacceptable drug-related toxicity, dosing of subjects already enrolled in the study may be continued or suspended pending further review. BioMarin will consult the DRB to aid in evaluating the risks of continuing the study and options for modification of the study to minimize subject risk.

Subjects who have a loss of 3 or more points on the combined motor and language components of the Hamburg CLN2 rating scale in any 1 year period may be discontinued at the discretion of the Investigator.

Subjects with a score of 0 on the combined motor and language components of the Hamburg CLN2 rating scale at two consecutive visits will be discontinued from treatment.

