10.3.1.9 Deaths

All deaths that occur during the AE reporting period (refer to Section 10.2.1), regardless of attribution, will be recorded on the AE eCRF and expeditiously reported to the Sponsor (in compliance with applicable regulations) as an SAE.

When recording a death, the event or condition that caused or contributed to the fatal outcome should be recorded as the single medical concept on the eCRF. If the cause of death is unknown and cannot be ascertained at the time of reporting, record "Unexplained Death" or "Death of Unknown Cause" on the eCRF. If the death is attributed to progression of the disease or condition being studied, record "progressive CLN2 disease" as the SAE term on the eCRF.

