10.4 Reporting Requirements

10.4.1 Expedited Reporting Requirements

All SAEs, AEoSI, and pregnancies that occur during the course of the AE Reporting Period (refer to Section 10.2.1), whether or not considered related to study drug, must be reported via eCRF to BioMarin Pharmacovigilance (BPV) within 24 hours of the site becoming aware of the event. If the eCRF system is not available, the SAE must be reported on the study-specific SAE report form and entered into eCRF when possible. If the AE/SAE is assessed as related to the device (or any of its components), in addition to the eCRF entry, the study-specific device report form must be completed and submitted via email/fax within 24 hours of the site becoming aware of the event. Investigators should not wait to collect information that fully documents the event before notifying BPV of an SAE. BioMarin may be required to report certain SAEs to regulatory authorities within 7 calendar days of being notified about the event; therefore, it is important that Investigators submit any information requested by BioMarin as soon as it becomes available.

The reporting period for SAEs begins after informed consent is obtained and continues until 6 months following either the last administration of study drug or study discontinuation/termination, whichever is longer (also see Section 10.2.1). The reporting period for device-related events begins with reservoir implantation and ends 4 weeks following removal of the implanted reservoir and catheter.

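### For a child who stops drug but stays on study, Protocol 10.2.1 and 10.4.1 end safety reporting on different dates, and a site applying 10.2.1 literally could leave late on-study events unreported

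*Protocol*

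**What the plan says.** The protocol states the end of safety reporting in several places.

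- **Section 10.2.1**, which defines the reporting period: "AE/SAE/pregnancy reporting should continue as detailed above until the safety follow-up visit occurs 6 months after the last administration of study drug". End of participation is not mentioned.
- **Section 10.3.1.9** borrows that period: "All deaths that occur during the AE reporting period (refer to Section 10.2.1), regardless of attribution, will be recorded on the AE eCRF".
- **Section 10.4.1** says two things. Its first paragraph covers "All SAEs, AEoSI, and pregnancies that occur during the course of the AE Reporting Period (refer to Section 10.2.1"). Its last paragraph says that the SAE period "continues until 6 months following either the last administration of study drug or study discontinuation/termination, whichever is longer".
- **Table 9.1.1, footnote w**, has all AEs and SAEs recorded "until 6 months after either the last administration of study drug or the Early Termination visit". It has no rule for choosing between the two dates.

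On scope, Section 10.2.1 requires all AEs after the first dose. It then says that, for children who do not enter an extension or registry, the 4-week and 6-month follow-up visits "will capture information regarding ongoing events at the time of the last dose or new events related to study drug". Footnote w and Sections 12.11 and 12.12 repeat that description.

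The protocol also provides for children who are off drug but still on study. Section 9.3.3 says "Subjects may suspend or discontinue study medication but should be encouraged to be evaluated per study-specific visit schedule". Section 9.3.3.1 says that a child with a combined motor-language score of 0 on the "rating scale at two consecutive visits will be discontinued from treatment". It does not say that the child leaves the study.

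**The concern.** If drug and study end together, all the rules point to nearly the same date. For a child who comes off drug and keeps attending, the section that defines the reporting period closes it while scheduled visits continue, and another section keeps it open for SAEs. Two sites could treat the same event differently, each with a protocol section in support.

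The children affected would have stopped because of toxicity, device trouble or disease progression. Their later SAEs and deaths bear directly on safety after stopping. The SAP does not settle the matter. Its Section 14.1 counts as treatment-emergent any AE that is new or worse after ICV surgery, with no upper cut-off. Whatever a site enters is tabulated and whatever it omits is absent, so a difference in how sites read the protocol would pass straight into the AE, SAE and death outputs.

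**Working it through.** The plan gives no figure to reproduce. The check is calendar arithmetic, followed by a comparison of the rules for deaths and for scope.

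**Inputs**

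- Study completion visit: Week 145 (Table 9.1.1, footnote on ICV device removal).
- Six months taken as 26 weeks.
- T, the week of last dose: an assumption, because the documents report no such child. Range shown: Week 1 to Week 119.
- The child attends to Week 145.

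**Formulas**

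- End under 10.2.1 = T + 26.
- End for SAEs under the last paragraph of 10.4.1 = 145 + 26 = Week 171.
- On-study weeks outside the 10.2.1 window = max(0, 145 - (T + 26)) = max(0, 119 - T).
- Distance between the two end dates = 171 - (T + 26) = 145 - T.

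| Last dose (T) | 10.2.1 ends | On-study weeks outside it | 10.4.1 ends (SAEs) | Difference (weeks) |
|---|---|---|---|---|
| Week 1 | Week 27 | 118 | Week 171 | 144 |
| Week 24 | Week 50 | 95 | Week 171 | 121 |
| Week 48 | Week 74 | 71 | Week 171 | 97 |
| Week 72 | Week 98 | 47 | Week 171 | 73 |
| Week 96 | Week 122 | 23 | Week 171 | 49 |
| Week 119 | Week 145 | 0 | Week 171 | 26 |

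The uncovered on-study time exceeds one year (52.18 weeks) only if 119 - T > 52.18, that is, T < 66.82, or a last dose before about Week 67. With Week 144 as the end, the threshold becomes T < 65.82.

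**Footnote w.** A child followed to Week 145 has a Study Completion visit, not an Early Termination visit. The footnote therefore does not clearly extend the period in this scenario. Only the last paragraph of 10.4.1 clearly does, and only for SAEs.

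**Deaths.** Take T = 48 and a death at Week 80. Section 10.3.1.9 uses the 10.2.1 window, which closed at Week 74, so the death falls outside it. Section 10.1.2 makes a fatal event an SAE, so the last paragraph of 10.4.1 (to Week 171) includes it. The first paragraph of 10.4.1 points back to 10.2.1. Section 10.6 does not resolve this: it applies after participation ends and only to events the investigator believes may be related to treatment.

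**Scope.** Up to the safety follow-up visit, 10.2.1 asks for all AEs. Its description of the follow-up visits names only events ongoing at the last dose and new drug-related events. A new unrelated event found at such a visit fits the first statement and not the second.

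**With one later-of rule throughout.** Reporting for a child followed to Week 145 runs to about Week 171 whatever T is, and the uncovered on-study time is 0 weeks.

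**The case against.** The strongest reply is that events would be recorded anyway. Section 9.7.3.1 has AEs asked about at each visit. Section 10.2.2 has investigators seek AEs, SAEs and AEoSI at each contact and record them, with no end date. Table 9.1.1 shows continuous monitoring. No passage tells a site to discard an event elicited at a visit. This stands. A reader might infer from 10.2.1 that more than a year of on-study events will go unrecorded, or that there is no AE reporting after the window closes. The documents do not support that, because eliciting and recording continue at every attended visit. What remains is that these sections disagree with the section that defines the period.

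A reader might also infer that a late on-study death is outside every rule. It is not: a death is an SAE, and the last paragraph of 10.4.1 covers it. The difficulty is that 10.3.1.9, and 10.4.1's own first paragraph, point the other way.

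Three narrower replies have force:

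- Device-related events have their own window, to 4 weeks after final removal (10.2.1, 10.4.1), and Section 10.5 has unresolved events followed up.
- The text on the follow-up visits does not say that they capture nothing else, so the scope point is an ambiguity, not a stated exclusion.
- Much of the protocol assumes that drug and study end close together. The completion or termination visit is timed from the last dose, and Section 9.3.3.1 lets participation resume after a suspension only within a limit on missed doses. That limit sits awkwardly with 9.3.3 and the two passages must be reconciled, but it does not cancel the 9.3.3 instruction to keep children attending off drug.

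**Conclusion.** The inconsistency is real and should be corrected. For a child off drug but on study, 10.2.1 and 10.3.1.9 close reporting six months after the last dose, 10.4.1 keeps it open for SAEs to six months after the end of study while also referring back to 10.2.1, and footnote w does not decide between its two dates.

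The on-study time affected is max(0, 119 - T) weeks. It is more than a year only for a last dose before about Week 67, and nil from about Week 119. This rests on an assumed week of last dose, attendance to Week 145, and six months taken as 26 weeks. The documents do not say how many children were in this position. SAP Appendix 3 allows for 14 matched pairs, so one child would be 1/14, about 7%.

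Loss of data is a risk at sites that apply 10.2.1 literally. It is not shown to have happened and is not certain to happen.

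**What to change.** Give Sections 10.2.1, 10.3.1.9 and 10.4.1 and Table 9.1.1 footnote w one end date, using the rule already in the last paragraph of 10.4.1: six months after the last dose or after the end of study participation, whichever is later. Apply it to all AEs, SAEs, AEoSI and deaths regardless of relationship. Keep the existing cut-off at first dose in a new BioMarin study or registry, and the separate window for device-related events. Align the description of the follow-up visits in 10.2.1, footnote w, 12.11 and 12.12 with that scope, so that it cannot be read as limiting new events to drug-related ones.

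If follow-up has already ended, query the sites about any child who stayed on study off drug, and state in the clinical study report which window was applied.

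The cost is protocol wording and a letter to sites. No visits are added, because AEs are already asked about at each one. The downside is slightly more AE entry for off-drug children.
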